18.4. LABORATORY EVALUATIONS

Results of continuous variables from the Q² Solutions Clinical Lab (QLAB) will be summarized in the reporting for Hematology, Serum Chemistry, Urinalysis (excluding the 24-hour urine), and 24-hour Urine Collection (excluding 24-hour urine protein). Similar to 24-hour urine protein, any other 24-hour parameters including 24-hour urine albumin and creatinine with a collection duration not equal to 24 hours will be adjusted to 24-hour. A list of laboratory parameters to be included in the outputs can be found below in Tables 3, 4, and 5. The lab results will be converted to SI units prior to any analysis and all presentations will be based on SI units.

Table 3 Serum Chemistry Parameters

Alanine aminotransferase (ALT)	Creatinine, serum
Alkaline phosphatase	Gamma – glutamyltransferase (GGT)
Aspartate aminotransferase (AST)	Glucose
Albumin	Lactate dehydrogenase (LDH)
Bilirubin, total	Magnesium

Document: \\quintiles.net\enterprise\Sites\CAMTL\IntProjects\SasData\Amicus\AT1001\AXA23225A\Biostatistics\Documentation\SAP\DR\Amicus_AT1001-042_SAP_Final_v1.0_20190821.docx

Author: Amicus

Version Number: Final v1.0

Version Date: 21AUG2019

Template No.: CS_TP_BS016 Revision 5

Reference: CS_WI_BS005

Effective Date: 01Apr2018

Blood urea nitrogen (BUN)	Phosphorous
Calcium, total	Potassium
Carbon dioxide, total (bicarbonate)	Protein, total
Chloride	Sodium
Alanine aminotransferase (ALT)	Creatinine, serum
Creatine phosphokinase	Low density lipoprotein (LDL) cholesterol
Uric acid	High density lipoprotein (HDL) cholesterol
Cystatin C	triglycerides

Table 4 Hematology Parameters

Platelet count	Automated WBC Differential:
RBC count	Neutrophils
WBC count (absolute)	Lymphocytes
Hematocrit	Monocytes
Hemoglobin	Eosinophils
	Basophils

Table 5 Urinalysis Parameters

Color	Ketones
Appearance	Blood
Specific gravity	WBC
pH	Nitrite

Document: \\quintiles.net\enterprise\Sites\CAMTL\IntProjects\SasData\Amicus\AT1001\AXA23225A\Biostatistics\Documentation\SAP\DR\Amicus_AT1001-042_SAP_Final_v1.0_20190821.docx

Author: Amicus

Version Number: Final v1.0

Version Date: 21AUG2019

Template No.: CS_TP_BS016 Revision 5

Reference: CS_WI_BS005

Effective Date: 01Apr2018

Protein	Bilirubin
Glucose	Microscopy of sediment

For parameters not having Baseline assessments, the data of last visit is imported from the previous study AT1001-012 and will serve as the baseline for this study.

Quantitative laboratory measurements reported as “< X”, e.g. below the lower limit of quantification (BLQ), or “> X”, e.g. above the upper limit of quantification (ULQ), will be converted to X for the purpose of quantitative summaries, but will be presented as recorded, e.g. as “< X” or “> X” in the listings.

Listings presenting lab results in each subcategory (e.g. Hematology, Serum Chemistry, Urinalysis, 24-hour Urine, Serum Pregnancy, and Urine Pregnancy) will be provided.

A listing of subjects with at least one assessment falling outside of the normal range will also be provided and clinical significance will be included in this listing.

A listing including all historical laboratory data will be provided.

18.4.1. LABORATORY REFERENCE RANGES AND CLINICAL SIGNIFICANCE

Quantitative laboratory measurements will be compared with the relevant laboratory reference ranges in SI units and categorized as:

- Low: Below the lower limit of the laboratory reference range.
- Normal: Within the laboratory reference range (upper and lower limit included).
- High: Above the upper limit of the laboratory reference range.

For reference range with a single boundary, there will be only two of the three categories presented for the parameter (either Low/Normal, or Normal/High), e.g. Magnesium concentration is deemed High if result > 1.25 mmol/L, and Normal if at or below 1.25 mmol/L.

For categorical results in Urinalysis, they will be categorized into two categories, i.e. Normal/Abnormal if the result is different from that of the normal reference value. Shifts from baseline to any post-baseline visit summary tables based on the Low/Normal/High categories (and the variants) described above will be provided.

In addition to the high and low quantitative laboratory assignments, any result deemed clinically significant by the PI will be captured in the eCRF, and will be presented in the summary tables.

Document: \\quintiles.net\enterprise\Sites\CAMTL\IntProjects\SasData\Amicus\AT1001\AXA23225A\Biostatistics\Documentation\SAP\DR\Amicus_AT1001-042_SAP_Final_v1.0_20190821.docx

Author: Amicus

Version Number: Final v1.0

Version Date: 21AUG2019

Template No.: CS_TP_BS016 Revision 5

Reference: CS_WI_BS005

Effective Date: 01Apr2018

18.5. 12 LEAD ECG (ECG) EVALUATIONS

Results from the central ECG (Electrocardiogram) Reading Centre will be included in the reporting of this study. The following ECG parameters will be reported in summary tables using descriptive statistics for this study:

- PR Interval (msec)
- QRS Interval (msec)
- QT Interval (msec)
- QTcF Interval (msec)
- HR (bpm)
- RR (msec)

All findings, including clinically significant findings, will be captured by the eCRF for the overall ECG evaluation, and categorized into Normal; Abnormal, NCS; and Abnormal, CS.

In addition to the change from baseline descriptive statistics summary, the number and percentage of subjects will be presented in a table for the overall ECG evaluation of clinical significance at any time of the study including unscheduled visits. A shift table by visits will also be constructed for change from baseline to post-baseline visits with regards to the three categories of the overall ECG evaluation.

A listing presenting all available ECG assessments will be provided. In addition, a listing of subjects with at least one clinically significant finding will be provided.

18.6. ECHOCARDIOGRAPHY (ECHO)

ECHO parameters are categorized into Normal, Mildly Abnormal, Moderately Abnormal, Severely Abnormal (or Low, Normal, High) by gender (or age) based on the criteria below for safety purpose, and a table presenting counts and percentages of each category by parameter and visit will be provided. A table presenting Severely Abnormal incidence at any visits through the study including unscheduled visits will be included.

ECHO Parameters	Criteria for Female	Criteria for Male	Abnormality Category
Left Ventricular Posterior Wall Thickness Diastole (cm) (LVPWTD)	0.6 - 0.9	0.6 - 1.0	Normal
	1.0 - 1.2	1.1 - 1.3	Mildly Abnormal

Document: \\quintiles.net\enterprise\Sites\CAMTL\IntProjects\SasData\Amicus\AT1001\AXA23225A\Biostatistics\Documentation\SAP\DR\Amicus_AT1001-042_SAP_Final_v1.0_20190821.docx

Author: Amicus

Version Number: Final v1.0

Version Date: 21AUG2019

Template No.: CS_TP_BS016 Revision 5

Reference: CS_WI_BS005

Effective Date: 01Apr2018

ECHO Parameters	Criteria for Female	Criteria for Male	Abnormality Category
	1.3 - 1.5	1.4 - 1.6	Moderately Abnormal
	≥ 1.6	≥ 1.7	Severely Abnormal
Intraventricular Septum Thickness Diastolic (cm) (IVSTD)	0.6 - 0.9	0.6 - 1.0	Normal
	1.0 - 1.2	1.1 - 1.3	Mildly Abnormal
	1.3 - 1.5	1.4 - 1.6	Moderately Abnormal
	≥ 1.6	≥ 1.7	Severely Abnormal
Left Ventricular Ejection Fraction (%) (LVEF)	≥ 55	Same as female	Normal
	45 - 54	Same as female	Mildly Abnormal
	30 - 44	Same as female	Moderately Abnormal
	< 30	Same as female	Severely Abnormal
Fractional Shortening (%) (FS)	27 - 45	25 - 43	Normal
	22 - 26	20 - 24	Mildly Abnormal
	17 - 21	15 - 19	Moderately Abnormal
	≤ 16	≤ 14	Severely Abnormal
Left Ventricular Mass (g) (LVM)	67 - 162	88 - 224	Normal
	163 - 186	225 - 258	Mildly Abnormal
	187 - 210	259 - 292	Moderately Abnormal
	≥ 211	≥ 293	Severely Abnormal
Left Ventricular Mass Index (g/m ²) (LVMI)	43 - 95	49 - 115	Normal

Document: \\quintiles.net\enterprise\Sites\CAMTL\IntProjects\SasData\Amicus\AT1001\AXA23225A\Biostatistics\Documentation\SAP\DR\Amicus_AT1001-042_SAP_Final_v1.0_20190821.docx

Author: Amicus

Version Number: Final v1.0

Version Date: 21AUG2019

Template No.: CS_TP_BS016 Revision 5

Reference: CS_WI_BS005

Effective Date: 01Apr2018

ECHO Parameters	Criteria for Female	Criteria for Male	Abnormality Category
	96 - 108	116 - 131	Mildly Abnormal
	109 - 121	132 - 148	Moderately Abnormal
	≥ 122	≥ 149	Severely Abnormal
Peak Mitral Inflow Velocity E (cm/s) (EPOINT)	For age < 50	Same as female	
	< 58	Same as female	Low
	58 - 86	Same as female	Normal
	> 86	Same as female	High
	For age ≥ 50	Same as female	
	< 48	Same as female	Low
	48 - 76	Same as female	Normal
	> 76	Same as female	High
Peak Mitral Inflow Velocity A (cm/s) (APOINT)	For age < 50	Same as female	
	< 30	Same as female	Low
	30 - 50	Same as female	Normal
	> 50	Same as female	High
	For age ≥ 50	Same as female	
	< 45	Same as female	Low
	45 - 73	Same as female	Normal
	> 73	Same as female	High

Document: \\quintiles.net\enterprise\Sites\CAMTL\IntProjects\SasData\Amicus\AT1001\AXA23225A\Biostatistics\Documentation\SAP\DR\Amicus_AT1001-042_SAP_Final_v1.0_20190821.docx

Author: Amicus

Version Number: Final v1.0

Version Date: 21AUG2019

Template No.: CS_TP_BS016 Revision 5

Reference: CS_WI_BS005

Effective Date: 01Apr2018

ECHO Parameters	Criteria for Female	Criteria for Male	Abnormality Category
Mitral Valve E/A Ratio (EARATIO)	For age < 50	Same as female	
	< 1.3	Same as female	Low
	1.3 - 2.5	Same as female	Normal
	> 2.5	Same as female	High
	For age >= 50	Same as female	
	< 0.8	Same as female	Low
	0.8 - 1.4	Same as female	Normal
	> 1.4	Same as female	High
Left Ventricular Internal Dimension at End Diastole (cm) (LVIDd)	3.5 - 5.3	4.2 - 5.9	Normal
	5.4 - 5.7	6.0 - 6.3	Mildly Abnormal
	5.8 - 6.1	6.4 - 6.8	Moderately Abnormal
	>= 6.2	>= 6.9	Severely Abnormal
Left Ventricular Internal Dimension at End Systole (cm) (LVIDs)	2.49 - 3.15	2.87 - 3.61	Normal
Midwall Fractional Shortening (%) (MWFS)	15 - 23	14 - 22	Normal
	13 - 14	12 - 13	Mildly Abnormal
	11 - 12	11	Moderately Abnormal
	<= 10	<= 10	Severely Abnormal

Systolic and diastolic function grading with respect to the abnormality categories are available in the data and will

Document: \\quintiles.net\enterprise\Sites\CAMTL\IntProjects\SasData\Amicus\AT1001\AXA23225A\Biostatistics\Documentation\SAP\DR\Amicus_AT1001-042_SAP_Final_v1.0_20190821.docx

Author: Amicus

Version Number: Final v1.0

Version Date: 21AUG2019

Template No.: CS_TP_BS016 Revision 5

Reference: CS_WI_BS005

Effective Date: 01Apr2018

be presented in the same table as parameters listed above.

ECHO comments and other information (parameters other than those listed above) will be presented in two other listings.

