4. STUDY DESIGN

4.1. GENERAL DESCRIPTION

This study is a multi-center, non-comparative, open-label, long-term extension study of migalastat HCl in subjects with Fabry disease who have completed treatment in a previous trial of migalastat HCl given as monotherapy. All subjects who were eligible for enrollment and completed migalastat HCl monotherapy treatment in a previous study, and who in the opinion of the investigator could benefit from remaining on migalastat HCl treatment were given the option to enroll into this trial. An alternative dosing regimen will be established per the addendum 1.1.2 for those

Document: \\quintiles.net\enterprise\Sites\CAMTL\IntProjects\SasData\Amicus\AT1001\AXA23225A\Biostatistics\Documentation\SAP\DR\Amicus_AT1001-042_SAP_Final_v1.0_20190821.docx

Author: Amicus

Version Number: Final v1.0

Version Date: 21AUG2019

Template No.: CS_TP_BS016 Revision 5

Reference: CS_WI_BS005

Effective Date: 01Apr2018

subjects with renal impairment (glomerular filtration rate (eGFR) < 30 mL/min/1.73m²), confirmed during the enrollment of the original protocol and amendment 1 and 1.1. The number of subjects to be enrolled in this study is expected to be up to 100, but is dependent on the number of eligible subjects completing migalastat HCl treatment in previous studies and who consent to enter this open-label extension study. Therefore, no sample size will be calculated.

The study will consist of a Baseline Visit (Visit 1) which will be performed at the time of the final visit of the previous study, followed by clinic visits every 6 months during the study. For the Addendum 1.1.2 subjects with renal impairment, clinical visits are performed approximately every 3 months. The duration of the treatment will vary among subjects and will continue until the date of regulatory approval or marketing authorization and/or commercialization in the participating subject's country, or study termination by the Sponsor, Amicus Therapeutics (Amicus).

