17.1.6. ECHOCARDIOGRAPHY (ECHO)

An ECHO will be performed at baseline, and every 12 months subsequently until the end of study visit, and the ECHO data will be collected in the EC domain. The following parameters will be summarized separately in tables

- LVM and LVMi
- Ejection Fraction
- Fractional Shortening
- LVIDd, LVIDs, MWFS, Wall Thickness.

These parameters will be presented to summarize the data by each visit for baseline, post-baseline and change from baseline. Supportive listings to these parameters will also be provided. ECHO parameters for safety evaluation is provided in the Safety Outcomes section.

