18. SAFETY OUTCOMES

The safety parameters include Adverse Events, Physical Examination, Vital Signs, Laboratory Tests, 12 Lead ECG, use of Concomitant Medications. All outputs for safety outcomes will be based on the ITT population using nominal visits (not including unscheduled visits and early termination) except tables presenting clinically significant results. These tables presenting clinically significant results will include unscheduled visits and early termination alongside the scheduled visits. Each continuous variable will be summarized for quantitative analysis using descriptive statistics by each visit including baseline, and change from baseline for that visit. Categorical variables will be summarized for qualitative analysis using incidence counts and percentages. The summary will be performed by each visit including baseline for each categorical parameter (e.g. Urinalysis parameters except pH and specific gravity).

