18.3. VITAL SIGNS

Vital Signs will be assessed at each study visit and results will be summarized descriptively by study visit for baseline, post-baseline visit and change from baseline.

The following Vital Signs measurements will be reported for this study:

- Sitting / Supine Systolic Blood Pressure (mmHg)
- Sitting / Supine Diastolic Blood Pressure (mmHg)
- Heart Rate (bpm)
- Respiratory Rate (breaths/min)
- Temperature (^oC)
- Weight (kg)
- Height (cm)
- BMI (kg/m²)

Body Mass Index (BMI) will be calculated using the same formula as baseline: BMI (kg/m²) = weight (kg)/ height (m)² of the same visit. It will be reported only for Baseline and Study Completion Visits.

Each measurement of the following parameters will be evaluated against the criteria of abnormality detailed below for potentially clinically significant vital signs. Potentially clinically significant vital signs are derived and categorized into PCS Low and PCS High, as well as Normal. In addition, a table summarizing the counts and percentages of each PCS category at any time including unscheduled visits will be presented.

Vital Signs	Criteria	Abnormality Categories
Pulse	≥ 120 bpm at any post-baseline time point and ≥ 15 bpm increase from baseline at any post-baseline time point	PCS High
	≤ 50 bpm at any post-baseline time point and ≥ 15 bpm decrease from baseline at any post-baseline time point	PCS Low
Systolic blood pressure	≥ 180 mm Hg at any post-baseline time point and ≥ 20 mm Hg increase from baseline at any post-baseline time point	PCS High
	≤ 90 mm Hg at any post-baseline time point and ≥ 20	PCS Low

Document: \\quintiles.net\enterprise\Sites\CAMTL\IntProjects\SasData\Amicus\AT1001\AXA23225A\Biostatistics\Documentation\SAP\DR\Amicus_AT1001-042_SAP_Final_v1.0_20190821.docx

Author: **Amicus** Version Number: **Final v1.0**
 Version Date: **21AUG2019**

Template No.: CS_TP_BS016 Revision 5 Reference: CS_WI_BS005

Effective Date: 01Apr2018

Vital Signs	Criteria	Abnormality Categories
	mm Hg decrease from baseline at any post-baseline time point	
Diastolic blood pressure	≥ 105 mm Hg at any post-baseline time point and ≥ 15 mm Hg increase from baseline at any post-baseline time point	PCS High
	< 40 mm Hg at any post-baseline time point and ≥ 15 mm Hg decrease from baseline at any post-baseline time point	PCS Low
Weight	≥ 7% change from baseline at any post-baseline time point	PCS High

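### The ECHO table of Severely Abnormal incidence (SAP 18.6) has no baseline restriction, so as worded it counts findings already present at Visit 1 as incidence

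*SAP*

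**What the plan says.** SAP 18.6 grades ECHO parameters into abnormality categories for safety and plans two tables. One gives category counts by parameter and visit. The other is described as follows: "A table presenting Severely Abnormal incidence at any visits through the study including unscheduled visits will be included". No condition on baseline is attached to the second table.

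The Baseline Visit is Visit 1 of this study (SAP 4.1), and it includes an ECHO. SAP 17.1.6 says: "An ECHO will be performed at baseline, and every 12 months subsequently until the end of study visit". The general rule in SAP 18 is: "These tables presenting clinically significant results will include unscheduled visits and early termination alongside the scheduled visits". It adds visits and does not take Baseline out.

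Other safety domains in the same SAP do refer to baseline. In 18.3, a high pulse is flagged only if it is "≥ 120 bpm at any post-baseline time point and ≥ 15 bpm increase from baseline at any post-baseline time point". Section 18.4.1 plans laboratory shifts from baseline. Section 18.5 plans a by-visit ECG shift table on its three evaluation categories. The supplied text lists no such table for the ECHO categories.

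**The concern.** Incidence normally means a finding that arises during observation. A count over all visits, Baseline included, is a period prevalence. Dropping the Baseline record alone would not cure this, because a severe finding that persists would be counted again at the first 12-month ECHO. The missing element is a new-onset condition.

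Long-term safety is the primary objective, and Protocol 8.2.1 lists ECHO among the safety assessments. Two features of the plan give this table extra weight:

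- By-visit safety summaries leave out unscheduled and early-termination data (SAP 18). The any-visit table is therefore the planned categorical ECHO summary that uses unscheduled examinations.
- Protocol 8.2.5 keeps clinically significant findings associated with the underlying disease out of AE reporting unless they are worse than expected. Some cardiac worsening may then appear mainly in the ECHO outputs.

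A reader who took the percentage as new severe abnormality during the extension could be misled about its size.

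**Working it through.** **Reading of the rules**

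| Domain | Post-baseline or baseline reference in the categorical summary? |
|---|---|
| Vital signs (18.3) | Yes: criteria use post-baseline values and a change from baseline |
| Laboratory (18.4.1) | Yes: shift tables from baseline |
| ECG (18.5) | Yes: shift table by visit, beside the any-time table |
| ECHO (18.6) | No: counts by visit and an any-visit count, with no shift table listed |

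**Example.** A woman with LVMi of at least 122 g/m² (149 g/m² for a man) is Severely Abnormal under 18.6. If she has that value at Visit 1 and at every later ECHO, she is counted as incidence although her category never changed.

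**Size.** The plan states no figure for this table, so there is nothing to reproduce. The following is an illustration.

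- N = 100, the upper number expected in Protocol 6.1.
- b = share Severely Abnormal at Baseline on a given parameter. Assumed, 0% to 30%.
- q = share of the remainder who become Severely Abnormal. Assumed, 2%, with 5% as a second value.
- All subjects are assumed to have a post-baseline ECHO.

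Any-visit percentage = [N·b + N·(1 − b)·q] / N

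New-onset percentage among those at risk = [N·(1 − b)·q] / [N·(1 − b)] = q

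Share of counted subjects already severe at Baseline = N·b / [N·b + N·(1 − b)·q]

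For b = 10% and q = 2%, the count is 10 + 90 × 0.02 = 11.8, so the table shows 11.8%. New onset is 1.8/90 = 2.0%, and 10/11.8 = 85% of those counted entered severe.

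| b | Table, q = 2% | New onset | Share severe at entry | Table, q = 5% | Share severe at entry |
|---|---|---|---|---|---|
| 0% | 2.0% | 2.0/100 = 2.0% | 0% | 5.0% | 0% |
| 5% | 6.9% | 1.9/95 = 2.0% | 72% | 9.8% | 51% |
| 10% | 11.8% | 1.8/90 = 2.0% | 85% | 14.5% | 69% |
| 20% | 21.6% | 1.6/80 = 2.0% | 93% | 24.0% | 83% |
| 30% | 31.4% | 1.4/70 = 2.0% | 96% | 33.5% | 90% |

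At b = 0 the two measures agree. Above that, the excess over q is b·(1 − q), so it is driven almost entirely by b, which the documents do not give.

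**The case against.** The strongest reply is that the information is already in the planned outputs. SAP 17.1.6 gives continuous change from baseline for the main ECHO parameters, with listings. Appendix 1 sorts listings by subject, parameter and date. The by-visit category table includes Baseline, so one could subtract the baseline-severe count from the any-visit count. Table templates also exist (SAP 9), are not in the supplied text, and may settle whether Baseline is counted. This largely stands against any claim that the plan cannot identify new cases. It does not replace a direct summary:

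- Subtraction works only if Baseline is counted, the any-visit table is by parameter, and both tables use the same baseline. Section 7.2 takes the last non-missing pre-dose value, unscheduled values included, whereas by-visit summaries use nominal visits (7.3).
- Section 7.6 divides by the whole population, so the at-risk denominator is missing.
- Mean changes do not count who crossed into a severe category.

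A second reply is that severe categories may be rare at entry. Exclusion criterion 6 bars clinically significant unstable cardiac disease, so a severe ejection fraction may well be uncommon. This stands for some parameters. No exclusion criterion sets a limit on LV mass, LVMi or wall thickness, however, so for these the question is open.

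A reader might also infer that the ECG table has the same fault, since it covers the "overall ECG evaluation of clinical significance at any time of the study including unscheduled visits". The documents do not support that. The table is not labelled as incidence, a baseline shift table on the same categories sits beside it, and exclusion criterion 11 names clinically significant ECG findings. That criterion also calls for discussion with the medical monitor, so a few such subjects could remain.

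**Conclusion.** The point holds for ECHO. As worded, SAP 18.6 labels as incidence a count that takes in unchanged baseline findings, and no categorical ECHO summary directly shows who became severe. That Baseline counts follows from the lack of any restriction, not from an explicit statement.

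The size is unknown. Under the assumed 2% new onset, the table would overstate by nothing if nobody is severe at Baseline and would show 31.4% if 30% are. These figures illustrate the mechanism and are not estimates for this trial.

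A reader might go further in two ways that the documents do not support. One is to say that baseline severity dominates the count, but no baseline ECHO distribution is given. The other is to say that the table reports Fabry disease at entry. Subjects come from an earlier migalastat study and are meant to continue treatment unbroken (SAP 7.2), so these are findings present at Baseline and cannot be assigned to the disease alone.

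**What to change.** In SAP 18.6, by parameter:

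1. Count a subject as incident only if a post-baseline ECHO (scheduled, unscheduled or early termination) is Severely Abnormal and the baseline category, with baseline as in 7.2, was not.
2. Use as denominator the subjects not Severely Abnormal at baseline who have at least one post-baseline ECHO.
3. Show subjects Severely Abnormal at baseline in a separate row.
4. Add a shift table from baseline category to worst post-baseline category.

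In 18.5, no redesign is needed. At most, add a sentence saying whether Baseline counts in the any-time ECG table.

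The data are already collected. The cost is SAP wording and one extra table, and the reported incidence percentages will be smaller wherever some subjects enter severe.
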